4.9 End of Study Treatment and Follow Up

After the last dose of study treatment, each patient will be followed for 28 days for adverse event monitoring (serious adverse events will be collected for 90 days after the end of treatment as described in Section 7.1). Patients removed from treatment for unacceptable adverse events will be followed until resolution or stabilization of the adverse event.

Patients who discontinue for reasons other than progressive disease will have post-treatment follow-up approximately every 3 months for disease status until disease progression, initiation of a non-study cancer treatment, withdrawal of consent or lost to follow-up.

After documented disease progression, each patient will be followed approximately every 3-6 months by review of medical records, telephone, or review of the Social Security Index for overall survival until death, withdrawal of consent, or the end of the study, whichever occurs first.

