2.3 Endpoints

Primary Endpoint:

1. Overall response rate (defined as complete or partial response) at 6 months based on RECIST.

Secondary Endpoints:

- 1. Duration of response, defined as time from documentation of tumor response to disease progression
- 2. Progression-free survival, defined as the time start of Avelumab until disease progression or death
- 3. Overall survival, defined as the time from start of Avelumab to death from any cause

- 4. Toxicity (grade 3 or higher), as defined by CTCAE 4.03.
- 5. Exploratory correlatives:
 - Tissue (new biopsy required upon study entry prior to therapy; repeat biopsy at time of progression will be encouraged but optional):
 - PDL1 expression by immunohistochemistry (ABC technique [Vector labs], using rabbit mAb 1:200 [Cell Signaling])
 - Immunophenotyping by flow cytometry:
 - T cell subsets (CD4, CD8, FOXP3)
 - Macrophages (CD68)
 - Cytokeratin 5/6 (by immunohistochemistry)
 - Peripheral blood (comparison of baseline and 12 week post-treatment samples, unless otherwise denoted)
 - TCR and BCR sequencing
 - T cell subsets (CD3, CD4, CD8, CD25, FOXP3)
 - B cells (CD19, CD20)
 - Macrophage I/II and myeloid-derived suppressor cells (MDSC) (CD16, CD68, CD206)
 - Natural killer cell activity (CD56, CD16)
 - EBV DNA plasma levels (will be performed at baseline, every 12 weeks after treatment initiation and at end of treatment)
- 6. Clinical activity of Avelumab as defined by overall response rate will also be measured utilizing immune-related RECIST.

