4.7.2 Pregnancy and Lactation

Pregnancy

Pregnancy must be excluded before the initiation of and during avelumab therapy, and prevented by the use of reliable contraception during treatment.

If a patient inadvertently becomes pregnant while on treatment with avelumab, the patient will immediately be removed from the study. The site will contact the patient at least monthly and document the patient's status until the pregnancy has been completed or terminated. The outcome of the pregnancy will be reported to the Study Chair and to Pfizer without delay and within 24 hours to the Study Chair and within 2 working days to Pfizer if the outcome is a serious adverse experience (e.g., death, abortion, congenital anomaly, or other disabling or life-threatening complication to the mother or newborn).

The study investigator will make every effort to obtain permission to follow the outcome of the pregnancy and report the condition of the fetus or newborn to the Study Chair. If a male patient impregnates his female partner the study personnel at the site must be informed immediately and the pregnancy reported to the Study Chair and to Pfizer and followed as described above.

Lactation

It is unknown if avelumab is secreted in breast milk. Breast-feeding must be discontinued during treatment with avelumab.

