4.10 Patient Withdrawal/Discontinuation from Study Criteria

Patients may be removed from study participation for the following reasons:

- The patient or legal representative withdraws consent for follow-up;
- The patient is lost to follow-up;
- The patient dies;
- It is the decision of the investigator.

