5.4 Follow-up Procedures

Patients discontinuing study treatment will be followed every three months after the last dose of study treatment until death with:

- Tumor assessments if they discontinued from study treatment without disease progression- until disease progression or initiation of a new anti-cancer therapy, and
- Survival contacts via medical record review, telephone call, or review of the Social Security Index.

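### Section 4.9 assigns survival follow-up only after documented progression and 4.10 lets the investigator end participation, while 4.1, 5.4 and the Schedule of Events follow every patient who stops treatment, so overall survival could be censored informatively

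*Combined protocol and SAP*

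**What the plan says.** Section 2.3 lists as a secondary endpoint "Overall survival, defined as the time from start of Avelumab to death from any cause". Section 9.4 plans Kaplan-Meier curves and medians with 95% confidence intervals and gives no censoring rule.

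Section 5.4 says: "Patients discontinuing study treatment will be followed every three months after the last dose of study treatment until death with" two items. The first is tumor assessments, for patients who stopped without progression. The second is "Survival contacts via medical record review, telephone call, or review of the Social Security Index", with no condition on progression. Section 4.1 likewise has all patients who discontinue followed every 3 months for both disease and survival. The Schedule of Events has a survival-contact row and a three-monthly follow-up column.

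Section 4.9 uses two tracks. Patients who stop for a reason other than progression are seen about every 3 months "for disease status until disease progression, initiation of a non-study cancer treatment, withdrawal of consent or lost to follow-up". Survival is taken up in the next paragraph: "After documented disease progression, each patient will be followed approximately every 3-6 months by review of medical records", telephone or the Social Security Index, "for overall survival until death, withdrawal of consent, or the end of the study, whichever occurs first".

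Section 4.10 lists the reasons for leaving study participation altogether. Besides withdrawal of consent for follow-up, loss to follow-up and death, it gives "It is the decision of the investigator", with no criteria and no mention of survival status.

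On pregnancy, section 4.7.2 says "the patient will immediately be removed from the study", whereas 4.8 lists a positive pregnancy test as a reason to stop study treatment.

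**The concern.** Kaplan-Meier estimation requires that a patient who is censored has the same later risk of death as one still followed. Patients who stop avelumab for toxicity or clinical decline and go on to another therapy, or whom an investigator takes off the study, may well not meet that condition. If one section keeps them in survival follow-up and another does not provide for it, their survival status depends on which section a site works from. There are seven sites, and the trial has a single arm, so there is no comparator in which the same distortion might partly cancel. A death not recorded at the time may be hard to recover later.

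**Working it through.** The point rests on wording, and no figure in the plan has to be reproduced.

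**The sections side by side**

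| | 4.1, 5.4, Schedule of Events | 4.9 |
|---|---|---|
| Who has survival follow-up | Every patient who stops treatment | Stated for patients with documented progression; no other group is mentioned |
| Interval | 3 months | About 3-6 months |
| End | Death (5.4) | Death, consent withdrawal or end of study |
| Tumor or disease-status follow-up without progression | Ends at progression or new therapy (5.4) | Same, plus withdrawal or loss |

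The rule for ending tumor follow-up therefore agrees. The differences are in the survival rows.

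**Tracing three patients through 4.9 and 4.10**

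1. Stops for toxicity, takes no new therapy. Stays in three-monthly disease-status follow-up under 4.9, and death is a progression-free survival event (2.3, 6.2.2). Little is lost.
2. Stops for toxicity or decline and starts another therapy before documented progression. The first track of 4.9 has ended and the second has not begun. Section 4.9 assigns this patient no survival follow-up; 5.4 does, until death.
3. Removed by the investigator under 4.10. Participation ends. That reason is not among the end points 4.9 gives for survival follow-up, and it cuts across the end point of death in 5.4.

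Case 2 is plausible: 4.8 allows stopping for adverse events, intercurrent illness or a changed condition, and scans are 12 weeks apart (4.1).

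**Illustration of size (all inputs assumed except n = 39)**

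Let survival be exponential with rate λ = ln 2 / m. A share s leaves follow-up at time L, and leavers then have hazard hλ. With full follow-up, for t beyond L,

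S(t) = (1 − s)·exp(−λt) + s·E[exp(−λL − hλ(t − L))].

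If leavers are censored at L, those remaining have hazard λ and the Kaplan-Meier median stays near m.

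Worked case: m = 12 months, so λ = 0.0578; s = 0.20; h = 2; L about 4.5 (middle of 3-6 months). At t = 10.9: 0.8 × 0.533 + 0.2 × 0.368 = 0.426 + 0.074 = 0.50. The full-follow-up median is about 10.9 months, against 12.0 with censoring. With h = 0.5, at t = 12.9: 0.8 × 0.475 + 0.2 × 0.605 = 0.380 + 0.121 = 0.50, so the median is about 12.9 and censoring understates it.

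Simulated medians in months, m = 12, leaving at 3-6 months:

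| Share leaving | Hazard of leavers | Full follow-up | Censored at leaving |
|---|---|---|---|
| 10% | half | 12.5 | 12.0 |
| 20% | half | 12.9 | 12.0 |
| any | equal | 12.0 | 12.0 |
| 10% | double | 11.4 | 12.0 |
| 20% | double | 10.9 | 12.0 |
| 30% | double | 10.4 | 12.1 |

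With m = 20 (scaled to the first-line figure of 19-21 months in section 1.1) and leaving at 2-8 months, the censored median is about 20 throughout. Full follow-up at 10% / 20% / 30% leaving gives 19.4 / 18.8 / 18.2 for h = 1.5, 18.9 / 17.8 / 17.0 for h = 2, and 18.2 / 16.7 / 15.3 for h = 3. About 3 to 10 of the 39 patients are then censored.

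**The case against.** The strongest reply is that the lost patient is already covered. Sections 4.1 and 5.4 and the Schedule of Events all provide survival contact after discontinuation, and section 5.0 points to the Schedule for procedures. Section 4.9 does not say that survival follow-up is confined to patients with progression; it is silent about the others, and a site can obey 4.9 and 5.4 together. A reader might infer that 4.9 excludes these patients, and the text does not support that. What remains is that 4.9 is the section on end of treatment and follow-up, it names one group, and its interval and end point differ outright from 5.4.

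Second, the exposed group is narrow: it takes stopping without progression and also switching before documented progression, or removal by the investigator. The documents give no rate for either. Section 1.6 reports grade 3 or higher treatment-related events in 10.7% of the pooled avelumab cohort, which is not a discontinuation rate, and nothing supports a share of 20-30%. Social Security Index review needs no visit and could recover some deaths. This stands.

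Third, a reader might infer that overall survival will be overstated by a definite amount. That is not supported: the direction reverses if leavers do better, and with 39 patients and a 12-month median the 95% sampling range of the estimated median is itself about 7 to 18 months.

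Fourth, 4.10 is permissive and pregnancy on study should be very rare, given the testing and contraception rules. Agreed for pregnancy, which is a matter of consistent wording only. For 4.10, permission without a provision for survival status is enough to leave the gap.

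**Conclusion.** The inconsistency is real and worth correcting. A site that follows 4.9 or 4.10 as written could stop recording survival status for patients whom 4.1, 5.4 and the Schedule of Events keep in follow-up. If their prognosis differs from that of patients still followed, the censoring is informative and the overall survival estimate could be biased up or down.

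The size cannot be derived from the documents. In the assumed scenarios it runs from zero, through 0.5 to 1.7 months either way in the 12-month setting, to an overstatement of about 5 months in the most extreme 20-month scenario (30% leaving with three times the hazard). These figures show how the bias depends on the share leaving and their hazard; they do not predict it.

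The consequence is limited to a descriptive secondary endpoint without a hypothesis or comparator. The primary response test and the two-stage decision rule in 9.2 do not use survival follow-up and are unaffected.

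**What to change.** - **4.9:** start survival follow-up for every patient who discontinues treatment, whatever the reason and including after a non-study cancer treatment. Use one interval and one end point, matching 5.4. If follow-up is meant to close at the end of the study, both sections must say so.
- **4.10:** state that removal by the investigator ends study treatment and visits, but that survival status is still collected from records unless the patient withdraws consent for follow-up.
- **4.7.2 and 4.8:** reconcile the wording on pregnancy, so that it is clear whether the patient leaves the study or study treatment, and whether survival status is still collected.
- **9.4:** add one sentence on how overall survival is censored.

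The cost is a wording amendment. The contacts it calls for are already required by 5.4, apart from a few record checks for patients removed under 4.10.

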4.10 Patient Withdrawal/Discontinuation from Study Criteria

Patients may be removed from study participation for the following reasons:

- The patient or legal representative withdraws consent for follow-up;
- The patient is lost to follow-up;
- The patient dies;
- It is the decision of the investigator.

5.0 STUDY PROCEDURES

Refer to the study Schedule of Events for procedures.

All patients will be closely monitored for safety and tolerability during all cycles of therapy, at study treatment completion/early study treatment discontinuation, and during the follow-up period.

5.1 Definitions of Study Assessments

a. Medical history

A medical history and details regarding the disease for which the patient has enrolled in this study will be obtained by the investigator or qualified designee. Medical history will include all active conditions, and any condition diagnosed within the prior 10 years that are considered to be clinically significant by the Investigator. Any clinically significant changes from Screening (e.g. worsening severity or abnormal findings) are considered to be adverse events (AEs).

b. Demographics

The patient's demographic profile of date of birth, gender, race, and ethnicity will be obtained unless the patient declines.

c. Review of eligibility criteria

Review of eligibility criteria as described in Section 3 to ensure patient qualification for study entry and adjuvant study treatment.

d. Concomitant Medication

All concomitant therapy, including anesthetic agents, vitamins, homeopathic/herbal remedies, nutritional supplements, received by patients from seven days prior to the first day of study treatment until 28 days after the last study dose (or until the start of a new treatment, whichever comes first) will be recorded in the patient's medical record. If a reportable adverse event deemed related to study intervention (see Section 7) occurs within 28 days after last study dose and the patient has not started a new treatment, recording of concomitant medications related to the treatment of that adverse event should continue until resolution of the adverse event.

e. Physical exam

The investigator or qualified designee will perform a complete physical examination during screening, which should include the evaluation of general appearance; evaluation of head, eyes, ears, nose, and throat (HEENT); and cardiovascular, pulmonary, abdominal, musculoskeletal, skin, lymph nodes, and neurological systems. Subsequent exams may be directed as appropriate.

Changes from baseline abnormalities should be recorded at each subsequent physical examination. New or worsened abnormalities should be recorded as adverse events if clinically significant.

f. Vital Signs and height

Vital signs should include temperature, pulse, blood pressure and weight. Height will only be collected at screening.

g. Performance status

Performance status is evaluated by the ECOG scale.

h. Adverse event assessment

Baseline assessment of subject status for determining adverse events. See Section 7 for Adverse Event monitoring and reporting.

i. Laboratory Assessments

Laboratory tests for hematology, chemistry, urinalysis, and others are specified in Table 5-1.

Table 5-1. Laboratory tests

Hematology	Complete Blood Count (CBC) with differential
	o hemoglobin,

	 hematocrit,
	 platelet count,
	 white blood cell count,
	 percentage or absolute differential count
Chemistry	Comprehensive metabolic panel (CMP)
	o albumin
	 alkaline phosphatase
	 aspartate aminotransferase (ALT)
	 alanine aminotransferase (AST)
	 bicarbonate (CO₂)
	 blood urea nitrogen (BUN)
	o calcium
	o chloride
	o creatinine
	∘ glucose
	 potassium
	o sodium
	 total protein
	 total bilirubin
	Thyroid stimulating hormone (TSH)
Pregnancy Test	Urine human chorionic gonadotropin (HCG) or serum βHCG
Urinalysis	o Blood,
-	o Glucose,
	o Protein,
	 Specific gravity
	 Microscopic exam (if abnormal)
If clinically	Hepatitis B: HepB sAg and/ or Hep B DNA
indicated	Hepatitis C: Hep C RNA PCR
	HIV
	••••

j. Blood collection for correlative studies

See Section 5.5 for details.

k. Tumor assessment

Radiologic assessment is performed by MRI with gadolinium or CT with contrast (neck and chest; abdomen/pelvis as indicated) or PET/CT. If a PET/CT is performed, the CT must be of diagnostic quality. The same radiographic technique should be used throughout the study. However, a patient who develops a contraindication to undergo an MRI scan during study treatment may remain on study and undergo contrast enhanced CT scans.

I. Tumor biopsy and tissue collection

See Section 5.5 for details.

5.2 Screening/Baseline Procedures

Assessments performed exclusively to determine eligibility for this study will be done only after obtaining informed consent. Assessments performed for clinical indications (not exclusively to determine study eligibility) may be used for baseline values even if the studies were done before informed consent was obtained.

All screening procedures must be performed within 21 days prior to registration unless otherwise stated. The screening procedures include:

- Written informed consent (within 28 days).
- Review of inclusion and exclusion criteria.

- Complete medical/oncology history.
- Demographics.
- Documentation of concomitant medications.
- Complete physical examination, including vital signs and height.
- Performance status assessment.
- Laboratory tests (within 7 days; pregnancy test within 72 hours).
- Blood collection for EBV DNA plasma levels and correlative studies.
- Documentation of tumor staging (imaging completed within 28 days).
- Tumor biopsy tissue collection for correlative studies (within 42 days).

5.3 **Procedures During Treatment**

5.3.1 Cycle 1 Day 1 (±3 days)

- Focused physical exam, including vital signs, ECOG performance status assessment and weight
- Assess for adverse events
- Update concomitant medications
- Collect blood samples for CBC with differential, CMP
- For patients with known hepatic metastases at time of study entry, liver function tests (including ALT, AST, total bilirubin, and alkaline phosphatase) must be performed once weekly for 7 weeks upon treatment initiation.

5.3.2 Each Additional Cycle, Day 1 (±3 days)

- Focused physical exam, including vital signs, ECOG performance status assessment and weight
- Assess for adverse events
- Update concomitant medications
- Collect blood samples for CBC with differential, CMP

5.3.3 Thyroid studies and Urinalysis (±3 days)

• Collect blood sample for TSH at cycle 2, cycle 4, then every 3 cycles thereafter (ie. cycle 7, 10 etc). Obtain urinalysis (dipstick) every 3 cycles following treatment initiation (ie. cycle 4, 7, 10 etc). Urine microscopic examination should be performed if dipstick abnormal.

5.3.4 Additional Blood Collection for Correlative Studies (±7 days)

- Collect blood sample to measure EBV DNA plasma levels every 3 cycles (ie. cycle 4, 7, 10 etc) and at end of treatment.
- Collect blood sample for additional correlative studies at 12 weeks after treatment initiation (ie. cycle 4).

5.3.5 Imaging (every 12 weeks ±7 days after treatment initiation)

- MRI, CT (neck and chest; abdomen/pelvis when indicated) or PET/CT (CT must be diagnostic quality)
- For patients who are clinically stable, a repeat scan will be required 4 weeks (±7 days) after initial radiographic findings of disease progression as a confirmatory assessment.

5.3.6 End of Treatment Visit (28 days after last dose, \pm 7 days)

- Focused physical exam, vital signs, ECOG performance status, weight
- Documentation of concomitant medications and adverse events.
- Collect blood samples for CBC with differential, CMP, TSH, EBV DNA plasma level.
- Collect urine sample for urinalysis.
- Optional tumor biopsy for patients who developed disease progression as reason for end of treatment

5.4 Follow-up Procedures

Patients discontinuing study treatment will be followed every three months after the last dose of study treatment until death with:

- Tumor assessments if they discontinued from study treatment without disease progression- until disease progression or initiation of a new anti-cancer therapy, and
- Survival contacts via medical record review, telephone call, or review of the Social Security Index.

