- 4. TSH monitoring will occur at baseline, cycle 2, cycle 4, then every 3 cycles thereafter (ie. Cycle 7,10 etc.), and at the end of treatment. For patients with asymptomatic TSH elevation, please refer to Section 4.3.1 for further evaluation. Specifically, if TSH < 0.5 x LLN, or TSH > 2 x ULN, or consistently out of range in 2 subsequent measurements: include T4 at subsequent cycles as clinically indicated; consider endocrinology consult.
- 5. Pregnancy test for females of child-bearing potential only.
- 6. Urinalysis (dipstick) will be performed at baseline, every 3 cycles following initiation of treatment (ie. Cycle 4, 7 and 10 etc.), and at the end of treatment. Urine microscopic examination should be performed if dipstick is abnormal.
- 7. EBV DNA plasma levels will be measured at baseline, every 3 cycles following initiation of treatment (ie. Cycle 4, 7, 10 etc.), and at end of treatment.
- 8. Newly obtained tumor tissue collection is mandatory upon study entry: See Section 5.5 for specifications. The study chair may grant exceptions to the mandatory biopsy should the treating physician deem that a biopsy is not feasible or unsafe for the patient, and archival tissue is available and provided for study purposes. A conversation with the study chair is required to obtain an exception. At time of disease progression, a repeat biopsy is encouraged but optional.
- 9. Blood for correlative studies should be collected at the same time blood is drawn for CBC and CMP if possible. 30 ml blood to be collected at baseline, at 12 weeks after treatment initiation (± 7 days). See Section 5.5.
- Imaging for radiographic disease assessment will be performed every 12 weeks following treatment initiation (± 7 days). The same imaging modality should be used throughout the study when feasible. For patients who are clinically stable, a repeat scan will be required 4 weeks (±7 days) after initial radiographic findings of disease progression as a confirmatory assessment. For CT or MRI, neck and chest should be evaluated; abdomen/pelvis as indicated. If a PET/CT is utilized, CT must be diagnostic quality.

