4.0 TREATMENT PLAN

4.1 Study Design

This is a prospective, multi-center, open-label, single-arm phase II trial to evaluate the efficacy of Avelumab for patients with recurrent/metastatic, EBV-related nasopharyngeal carcinoma. A total of 39 patients will be eligible to enroll. Patients will be enrolled at 7 sites: UC San Diego Moores Cancer Center, Stanford Cancer Institute, UC Los Angeles Jonsson Comprehensive Cancer Center, UC Irvine Chao Cancer Center, University of Southern California Norris Comprehensive Cancer Center, Providence Cancer Center, and Dana-Farber Cancer Institute.

All patients providing informed consent will be screened for eligibility. Baseline assessments will include vital signs, physical exam, ECOG performance status evaluation, blood hematology and chemistries, urinalysis and tumor imaging. Upon study entry, all patients will receive Avelumab 10mg/kg IV on days 1 and 15 of each 28-day cycle. Treatment will be given until disease progression, unacceptable toxicity, investigator decision or patient withdrawal. Dose reductions and/or interruptions may occur per pre-specified criteria for grade 3 or higher toxicity.

History and physical examination, adverse event assessment and routine bloodwork will be performed prior to every cycle. For patients with known hepatic metastases at time of study entry, liver function tests (including ALT, AST, total bilirubin, and alkaline phosphatase) must be performed once weekly for 7 weeks upon treatment initiation. All patients will undergo imaging (CT, MRI, or PET/CT [CT must be diagnostic quality]) within 4 weeks prior to study entry, 12 weeks after treatment initiation (+/- 7 days), and then every 12 weeks thereafter (+/-7 days). Response will be assessed using RECIST. For patients who are clinically stable, a repeat scan will be required 4 weeks (+/- 7 days) after initial radiographic findings of disease progression as a confirmatory assessment.

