A newly obtained tumor specimen will be obtained prior to study entry (unless it is not feasible or deemed unsafe for the patient, archival tissue is available, and study chair has granted an exception) for the purposes of measuring PD-L1 expression, T cell subsets etc. Patients will also provide blood samples at baseline and 12 weeks after treatment initiation for correlative studies, including PBMCs, T and B-cell subsets, frequency and clonality. Peripheral blood will be collected at baseline, and then every 12 weeks after treatment initiation as well as at end of treatment for serial measurement of EBV plasma DNA levels. Additionally, at time of disease progression, patients will be encouraged but not mandated to undergo a second biopsy for study purposes to permit further correlative studies.

An end of treatment visit for clinical evaluations and safety assessments will be performed approximately 28 days (\pm 7 days) after the last dose of study drug. Patients discontinuing study treatment will be followed every 3 months for disease and survival outcomes.

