9.2 Sample Size and Primary Analysis

A Simon's optimal two-stage design will be used for this cohort. The primary endpoint is overall response (CR or PR) rate at 6 months based on RECIST. If the overall response rate is $\leq 15\%$, we will consider the treatment as not meeting the threshold of going further. We will test the null hypothesis H0: $p \leq 15\%$ against the alternative hypothesis H1: p > 15%, where p is the overall response rate after six months of study treatment. The two-stage design proposed below will have an 80% power to reject the null hypothesis and conclude that the true overall response rate is above 15\%, if the observed overall response rate is $\geq 30\%$, at 10% significance level. The study design is described in detail is as follows:

Stage 1: 19 subjects will be accrued; accrual will be held until the progression results for all the 19 subjects are known for the first six months. The trial will be terminated at Stage 1 if \leq 3 of the 19 subjects have any CR/PR by 6 months; otherwise it will continue to Stage 2.

Stage 2: 20 more patients will be accrued. We will reject the therapy if, among all the 39 (19+20) subjects, the number of patients who have an overall response is ≤ 8 ; if ≥ 9 patients have a defined response by RECIST, the treatment will be successful. It will be concluded that our study treatment is associated with an overall response in more than 15% of patients.

Early stopping probability: Under this design, if the null hypothesis is true, the probability of stopping the trial early will be 68.4%. The sample size calculation was done using PASS version 8.0.16 (released January 27, 2011).

Final efficacy analysis will calculate the UMVUE estimate, p-value and 95% CI for the response rates.³²⁻³³ The calculation will be performed using R *clinfun* package (www.r-project.org).

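### Imaging after stopping avelumab without progression has conflicting anchors; under section 5.4 some patients have no scan near the 6-month primary time point

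*Combined protocol and SAP*

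**What the plan says.** While a patient is on treatment the rule is clear. Under Procedures During Treatment the heading is "5.3.5 Imaging (every 12 weeks ±7 days after treatment initiation"), which gives scans at weeks 12, 24 and 36.

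For a patient who stops without progression, the texts differ:

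- Section 5.4: "Patients discontinuing study treatment will be followed every three months after the last dose of study treatment until death with" two items, the first being "Tumor assessments if they discontinued from study treatment without disease progression- until disease progression or initiation of a new anti-cancer therapy, and". The clock starts at the last dose.
- Section 4.1, in a sentence about all patients: "12 weeks after treatment initiation (+/- 7 days), and then every 12 weeks thereafter (+/-7 days"). The clock starts at treatment initiation.
- Schedule of Events, imaging footnote: "Imaging for radiographic disease assessment will be performed every 12 weeks following treatment initiation (± 7 days"). This has the same anchor and is not limited to patients on drug.
- Section 4.1, closing paragraph: "Patients discontinuing study treatment will be followed every 3 months for disease and survival outcomes". No anchor is given.
- Section 4.9: "Patients who discontinue for reasons other than progressive disease will have post-treatment follow-up approximately every 3 months for disease status". No anchor is given.

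The End of Treatment visit (5.3.6) lists no scan. Section 9.2 states: "The primary endpoint is overall response (CR or PR) rate at 6 months based on RECIST". The Stage 1 rule in the same section counts any response reached by 6 months. Progression-free survival at 6 and 12 months is a secondary objective (2.2).

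**The concern.** Section 5.4 is the only section that both specifies off-treatment tumor assessments and gives them a starting point. A coordinator handling a patient who stopped for toxicity would naturally go there and count three months from the last dose. The next scan can then fall well after 6 months, although the initiation clock would have given one at week 24. With seven sites and no statement of which text governs, two schedules can run side by side.

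Three things are at stake. Response status at 6 months may be unobserved in these patients. Progression in the gap is recorded at the late scan, which pushes 6-month PFS upward. And the decisions turn on single patients: 3 versus 4 responders of 19 at Stage 1, and 8 versus 9 of 39 at the end.

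**Working it through.** **Inputs.** Doses fall on days 1 and 15 of 28-day cycles (4.1), so last doses are at weeks 0, 2, 4 and so on. On-treatment scans are at weeks 12 and 24 (5.3.5). Off-treatment scans under 5.4 come at the last dose plus 3 months, then every 3 months. Three months is 365.25/4/7 = 13.04 weeks; 6 months is 26.09 weeks. The documents give no window for the 6-month assessment. I assume weeks 23 to 27.1, that is, the week-24 scan less 7 days up to 6 months plus 7 days.

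**Scan dates under 5.4** (scan week = last-dose week + 13.04k, k = 1, 2):

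| Last dose (week) | On-treatment scans | Off-treatment scans | Scan in weeks 23-27.1? |
|---|---|---|---|
| 0 | none | 13.0, 26.1 | yes |
| 2 | none | 15.0, 28.1 | no |
| 4 | none | 17.0, 30.1 | no |
| 6 | none | 19.0, 32.1 | no |
| 8 | none | 21.0, 34.1 | no |
| 10 | none | 23.0, 36.1 | yes, at the edge |
| 12 | 12 | 25.0, 38.1 | yes |
| 14 | 12 | 27.0, 40.1 | borderline |
| 16 | 12 | 29.0, 42.1 | no |
| 18 | 12 | 31.0, 44.1 | no |
| 20 | 12 | 33.0, 46.1 | no |
| 22 | 12 | 35.0, 48.1 | no, unless scanned at week 24 before stopping |
| 24 | 12, 24 | 37.0, 50.1 | yes |

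For last doses at weeks 16-22 the interval after the week-12 scan is 29 - 12 = 17 to 35 - 12 = 23 weeks, against a planned 12, and the scan comes 3 to 9 weeks after 6 months. If 3 months is read as 12 weeks, last doses at weeks 16-22 still miss the window (scans at weeks 28-34), and the early group that misses it becomes weeks 4-10.

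**Scan dates on the initiation clock.** Every patient off treatment without progression has a scan at week 24 (weeks 23-25), whatever the last-dose date.

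**Effect on response.** If status is read at 6 months, it is unobserved for the affected patients. If any response by 6 months counts, a response already seen stands. What is lost is a first response arising after the last scan before 6 months, and timely confirmation. Appendix A, 2.4.1, requires confirmation in a non-randomized trial with response as the primary endpoint. The only repeat scan the protocol body schedules is for progression (5.3.5).

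**Effect on PFS.** Take a last dose at week 18 and progression at week 20. The 5.4 scan is at 18 + 13.04 = 31.0, so the patient counts as progression-free at 6 months. On the initiation clock it would be seen at week 24. One patient of 39 is 1/39 = 2.6 percentage points.

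**Design figures, reproduced.** For the rule of 3/19 then 8/39, with X1 ~ Bin(19, p) and X2 ~ Bin(20, p):

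- Early stopping at p = 0.15: P(X1 ≤ 3) = 0.684, matching the stated 68.4%.
- Type I error: P(X1 ≥ 4 and X1 + X2 ≥ 9 at p = 0.15) = 0.097, within 10%.
- Power at p = 0.30: 0.803, matching the stated 80%.

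**Illustration only.** Suppose a share q of true responders is missed and counted as non-responders. Both q and the counting rule are assumptions. Then p = 0.30(1 - q), and expected lost responders are 39 × 0.30 × q:

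| q | p | Lost responders | Power |
|---|---|---|---|
| 0 | 0.3000 | 0 | 0.803 |
| 2.5% | 0.2925 | 0.3 | 0.777 |
| 5% | 0.2850 | 0.6 | 0.749 |
| 10% | 0.2700 | 1.2 | 0.687 |

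Missing responders can only lower the counts, so type I error does not rise.

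**The case against.** A reader might infer that these patients simply have no scheduled 6-month scan. The documents do not support that. Section 4.1 speaks of all patients and the Schedule footnote is not limited to those on drug; under either, a patient who stops at week 18 is due a scan at week 24. The words about the last dose in 5.4 can also be read as describing the follow-up period rather than resetting the scan clock. This stands, and it is why the defect is an unreconciled anchor.

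A reader might also infer that unscanned patients count as non-responders, so that the primary rate is biased down. Section 9.1 only defines the ITT population as all enrolled patients; no rule for a missing assessment is given. Under the Stage 1 wording a response seen at week 12 is not erased unless confirmation is outstanding. Section 6.2.1 moreover ends best overall response at the end of treatment, so it is unclear whether an off-treatment scan would count at all. The loss of response information is therefore narrower than the scan gap.

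The power figures are not estimates: the documents give no rate of stopping without progression, and nothing shows that the affected group reaches 2.5% to 10% of responders. Appendix A (2.3.4) also urges every effort to document progression after treatment stops, in its paragraph on symptomatic deterioration. That could shorten some gaps, but it sets no dates. The follow-up column of the Schedule, which shows only a survival contact, is weak evidence, because the extracted imaging row does not mark later on-treatment scans either.

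None of this says which clock governs, and the only section that anchors off-treatment scans specifically uses the last dose.

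**Conclusion.** The point holds as a conflict between stated rules, with a real consequence if 5.4 is followed. Last doses at weeks 16-22 then leave no scan from week 12 until about weeks 29-35, and last doses at about weeks 2-8 give scans on either side of 6 months but none near it. Week 14 is borderline, and a patient last dosed at week 22 may already have the week-24 scan. These ranges rest on 3 months being 13.04 weeks and on my assumed window.

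Six-month PFS would be biased upward in affected patients, provided progression is dated at the scan that shows it. The effect on the primary rate depends on whether response is read at or by 6 months and on a counting rule the plan does not give. The number of patients affected is unknown. This should be corrected; it does not undermine the design figures, which reproduce.

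**What to change.** Reconcile 4.1 (both statements), 4.9, 5.3.5, 5.4 and the Schedule footnote to one rule: patients who stop study treatment without progression continue imaging every 12 weeks (±7 days), counted from treatment initiation, until progression or new anti-cancer therapy. Mark imaging in the follow-up column of the Schedule. Survival contacts may stay timed from the last dose.

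To complete the repair, state in 9.2 the window for the 6-month assessment, whether off-treatment scans count toward response, and how a patient with no scan in the window is counted.

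The cost is a sentence in each section and one mark in the Schedule. Scan frequency is essentially the same (12 against about 13 weeks), and sample size, type I error and power do not change. The one practical downside is that scan dates separate from the follow-up contacts timed from the last dose.
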